6.1.6 Pregnancy

Pregnancy in a study subject must be reported to AbbVie within 1 working day of the site becoming aware of the pregnancy. Subjects who become pregnant during the study must be discontinued (Section 5.4.1).

Information regarding a pregnancy occurrence in a study subject and the outcome of the pregnancy will be collected.

Pregnancy in a study subject is not considered an adverse event. However, the medical outcome of an elective or spontaneous abortion, stillbirth or congenital anomaly is considered a serious adverse event and must be reported to AbbVie within 24 hours of the site becoming aware of the event.

6.2 Product Complaint

6.2.1 Definition

A Product Complaint is any Complaint (see Section [6.0](#) for the definition) related to the biologic or drug component of the product or to the medical device component(s).

For a product this may include, but is not limited to, damaged/broken product or packaging, product appearance whose color/markings do not match the labeling, labeling discrepancies/inadequacies in the labeling/instructions (example: printing illegible), missing components/product, device not working properly, or packaging issues.

For medical devices, a product complaint also includes all deaths of a patient using the device, any illness, injury, or adverse event in the proximity of the device, an adverse event that could be a result of using the device, any event needing medical or surgical intervention including hospitalization while using the device and use errors.

Any information available to help in the determination of causality by the device to the events outlined directly above should be captured.

6.2.2 Reporting

Product Complaints concerning the investigational product and/or device must be reported to the Sponsor within 24 hours of the study site's knowledge of the event via the Product Complaint form. Product Complaints occurring during the study will be followed-up to a satisfactory conclusion. All follow-up information is to be reported to the Sponsor (or an authorized representative) and documented in source as required by the Sponsor. Product Complaints associated with adverse events will be reported in the study summary. All other complaints will be monitored on an ongoing basis.

Product Complaints may require return of the product with the alleged complaint condition (syringe). In instances where a return is requested, every effort should be made by the investigator to return the product within 30 days. If returns cannot be

accommodated within 30 days, the site will need to provide justification and an estimated date of return.

The description of the complaint is important for AbbVie in order to enable AbbVie to investigate and determine if any corrective actions are required.

7.0 Protocol Deviations

AbbVie does not allow intentional/prospective deviations from this protocol unless when necessary to eliminate an immediate hazard to study subjects. The principal investigator is responsible for complying with all protocol requirements, and applicable global and local laws regarding protocol deviations. If a protocol deviation occurs (or is identified) after a subject has been enrolled, the principal investigator is responsible for notifying Independent Ethics Committee (IEC)/Institutional Review Board (IRB) regulatory authorities (as applicable), and the following AbbVie Clinical Monitor(s):

Primary Contact:

Alternate Contact:

Such contact must be made as soon as possible to permit a review by AbbVie to determine the impact of the deviation on the subject and/or the study.

See [Appendix D](#) for Japan specific requirements.

8.0 Statistical Methods and Determination of Sample Size**8.1 Statistical and Analytical Plans****8.1.1 Datasets for Analysis**

The analysis set consists of all subjects who enrolled into this OLE study and received at least one dose of open-label study drug. This analysis set will be the primary analysis population for both efficacy and safety analysis.

8.1.2 Subject Accountability

The number of subjects who received at least 1 dose of study drug, the number of subjects who completed the study, and the number of subjects who prematurely discontinued will be summarized overall and by site.

8.1.3 Demographic and Baseline Characteristics

Demographic and baseline disease characteristics endpoints from Study 1311.5 will be summarized descriptively. Summary statistics for continuous variables will include the number of observations, mean, standard deviation, median, Q1, Q3 and range for continuous variables; frequencies and percentages for the discrete variables.

8.1.4 Subject Disposition and Study Drug Exposure**8.1.4.1 Subject Disposition**

The number and percentage of subjects who are enrolled and received at least one dose of study drug, and the number of subjects who prematurely discontinued and the reason for premature discontinuation will be summarized. Premature discontinuation of study drug will be summarized with frequencies and percentages overall and by reason for discontinuation for all subjects who received at least one dose of study drug. Subjects may have multiple reasons for prematurely discontinuing study drug, but will be counted no more than once for the total ("Any Reason").

8.1.4.2 Study Drug Exposure

Extent of exposure to study drug will be summarized for all subjects who received at least one dose of study drug in Study M16-244. The duration (days) of study treatment will be summarized with the mean, standard deviation, median, Q1, Q3 and range. The duration of treatment is defined as the difference between the dates of the first and last doses of the treatment plus 1 day.

8.1.5 Efficacy Analysis

The baseline for all efficacy analysis in this study will be the baseline in Study 1311.5.

8.1.5.1 Efficacy Variable

Please see Section [5.3.3](#) for the list of all efficacy endpoints in this study.

A subject will be considered an ACR20/50/70 responder if compared to the baseline in Study 1311.5.

1. The counts for both SJC (66 joints count) and TJC (68 joints count) have reduced by 20%/50%/70% or more; and
2. At least three of the five remaining ACR core set measures show reduction of 20%/50%/70% or more in:
 - a. Patient's Assessment of PsA Pain Intensity (VAS)
 - b. Patient's Global Assessment of Disease Activity (PtGA)
 - c. Physician's Global Assessment of Disease Activity (PhGA)
 - d. Patient's Assessment of Physical Function by Heath Assessment Questionnaire – Disability Index (HAQ-DI)
 - e. High sensitivity C-reactive protein

The other efficacy endpoints will be defined in details in Statistical Analysis Plan (SAP).

8.1.5.2 Efficacy Analysis

The efficacy analyses will be conducted with the analysis set described in Section [8.1.1](#).

For binary endpoints, frequencies and percentages will be calculated with 95% confidence intervals at each post-baseline time point. For the change from baseline measurement, the mean with 95% CI, standard deviation, median, Q1, Q3 and range will be reported at each post-baseline time point.

8.1.5.3 Multiple Comparisons

Not applicable.

8.1.6 Safety Analysis**8.1.6.1 General Considerations**

All subjects who receive at least one dose of study drug in this OLE study will be included in the safety analysis.

Incidence of adverse events, serious adverse events, premature discontinuation, and changes in vital signs, physical examination results, and clinical laboratory values will be analyzed for Study M16-244.

Treatment-emergent adverse events (TEAEs) will be tabulated by system organ class (SOC) and Preferred Term (PT).

Mean change from baseline for laboratory and vital signs data will be summarized. Baseline for vital signs, physical examination results, and clinical laboratory results for subjects will be the data collected at the Week 0 visit immediately prior to study drug administration in Study 1311.5.

Missing safety data will not be imputed.

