5.2 Selection of Study Population

5.2.1 Inclusion Criteria

1. Subjects who have completed all doses of study drug and Week 24 visit of Study 1311.5.
2. Women of childbearing potential must agree to use at least one of the following methods of contraception throughout the study including 20 weeks after the last study drug dose is given.
 - combined (estrogen and progestogen containing) hormonal birth control (oral, intravaginal, transdermal) associated with inhibition of ovulation initiated at least 1 month prior to study participation.
 - progestogen-only hormonal birth control (oral, injectable, implantable) associated with inhibition of ovulation initiated at least 1 month prior to study participation.
 - bilateral tubal occlusion/ligation
 - intrauterine device (IUD)
 - intrauterine hormone-releasing system (IUS).
 - Vasectomized sexual partner(s) (the vasectomized partner(s) should have received medical assessment of the surgical success and is the sole sexual partner of the trial participant).

- True abstinence: Refraining from heterosexual intercourse when this is in line with the preferred and usual lifestyle of the subject (periodic abstinence [e.g., calendar, ovulation, symptothermal, post-ovulation methods] and withdrawal are not acceptable).

Women of childbearing potential are defined as having experienced menarche and are:

- not postmenopausal (12 months with no menses without an alternative medical cause) and are
- not permanently sterilized (e.g., hysterectomy, bilateral oophorectomy or bilateral salpingectomy).

3. Women of childbearing potential must have a negative urine pregnancy test at Baseline (Week 0/V1).
4. Subjects must voluntarily sign and date an informed consent, approved by an Independent Ethics Committee (IEC)/Institutional Review Board (IRB), prior to the initiation of any study specific procedures.
5. Subject is judged to be in good health as determined by the Investigator.

See [Appendix D](#) for inclusion criterion specific to France.

Rationale for the Inclusion Criteria:

- 1, 5 To select the adequate subject population
- 2, 3 The impact of risankizumab on pregnancy and reproduction is unknown
- 4 In accordance with harmonized Good Clinical Practice (GCP)

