5.2.2 Exclusion Criteria

A subject will not be eligible for study participation if he/she meets any of the following criteria:

1. Female subject who is pregnant, breastfeeding or is considering becoming pregnant during study participation, including 20 weeks after the last dose of study drug is given.
2. Premature discontinuation of study drug in Study 1311.5 for any reason.
3. Use of a biologic treatment other than risankizumab since first dose of study drug in Study 1311.5.
4. Time elapsed is > 8 weeks since the Week 24 visit in Study 1311.5.
5. Active systemic infections during the last 2 weeks (exception: common cold) prior to randomization, as assessed by the investigator.
6. Anticipated requirement during the study or receipt of any live or attenuated vaccine since first dose administered in Study 1311.5.
7. Participation in another investigational study since first dose of study drug in Study 1311.5.
8. Current diagnosis of a major chronic inflammatory or connective tissue disease other than PsA (e.g., rheumatoid arthritis, systemic lupus erythematosus, ankylosing spondylitis, Lyme disease, gout) and fibromyalgia as assessed by the Investigator.
9. Use of any restricted medication as specified in this protocol or any drug considered likely to interfere with the safe conduct of the study, as assessed by the investigator, since first dose of study drug in Study 1311.5.
10. History of allergy/hypersensitivity to a systemically administered biologic agent or its excipients.
11. Chronic or relevant acute infections including HIV (human immunodeficiency virus), viral hepatitis and (or) active tuberculosis.
12. Any documented active or suspected malignancy or history of malignancy since first dose of study drug in Study 1311.5, except appropriately treated basal or squamous cell carcinoma of the skin or in situ carcinoma of uterine cervix.

13. Major surgery (including weight loss surgery), performed since first dose of study drug in Study 1311.5 or planned while study is ongoing as assessed by the investigator.

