## 6.0 Analysis Conventions

### 6.1 Definition of Baseline

The last non-missing measure collected on or before the day of the first dose of study drug injection in Study 1311.5 for each randomized subject will be used as the Baseline for summary of demographics, disease characteristics and safety analyses. For efficacy endpoints except modified total Sharp score (mTSS), the baseline is defined as the last non missing pre-treatment observation prior to first dose in Study 1311.5. The Baselines for mTSS are defined as the last non-missing observation prior to Day 13 and closest to Day 1 in Study 1311.5.

For mTSS, data for Week 24 in Study 1311.5 and Week 24 in Study M16-244 are considered in analyses. In the context of visits corresponding to mTSS data collection

they will be referred to as Week 24 (Study 1311.5) and Week 24 (Study M16-244) respectively.

If multiple measurements are recorded on the same day, the worst of the multiple measurements will be used.

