#### 5. **TEAEs by Preferred Term in Descending Frequency**

TEAEs, SAEs, and TEAEs leading to discontinuation of study drug will be summarized by prior and current treatment group in decreasing order of frequency of MedDRA PT in the total risankizumab doses, including AEs occurring after the first dose in Study M16-244 for subjects who received Placebo in Study 1311.5, as well as the highest dose arm from Study 1311.5. The most frequent TEAEs, SAEs and TEAEs leading to discontinuation of study drug can be identified from this summary.

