### **11.3 Analysis of Laboratory Data**

Changes from Baseline in Study 1311.5 in continuous laboratory parameters will be summarized by n, mean, standard deviation, minimum value, median, and maximum value for the group of subjects that received Placebo in Study 1311.5 and for the group of subjects that received Risankizumab in Study 1311.5.

Shift tables from Baseline to the final value (the last assessment during each treatment period) according to the normal range will be provided for each hematology, clinical chemistry parameter and urinalysis parameter. The laboratory data will be categorized as low, normal, or high based on the normal ranges of the laboratory used in this study. The shift tables will tabulate the number and percentage of subjects with Baseline in Study 1311.5 values below/within/above the normal range versus final values below/within/above the normal range.

Frequencies and percentages of subjects with post Baseline lab values meeting the following criteria in [Table 15](#) and [Table 16](#) will be summarized.

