### 11.4.2 Statistical Methods

Changes from Baseline in Study 1311.5 to each visit and to the final value in vital sign parameters will be summarized with the mean, standard deviation, median, minimum, Q1, Q3 and maximum. The Baseline and final value means will also be presented for subjects who have both the Baseline and final values (see Section 6.0 for the definition of Baseline and final values).

For systolic blood pressure, diastolic blood pressure and pulse, a listing of all subjects with any vital sign value meeting criteria for potentially clinically significant values will be provided. For each of these subjects, the whole course of the respective parameter will be listed. The number and percentage of subjects who have at least one value meeting criteria for potentially clinically significant values will be provided for each selected vital sign parameter.

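### For subjects who had placebo in Study 1311.5, laboratory and vital-sign changes start nominally 24 to 32 weeks before the first risankizumab dose, so change, shift and Table 18 results mix pre-drug with on-drug change

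*Protocol*

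**What the plan says.** Protocol 8.1.6.1 sets one safety baseline for everyone: the baseline for "clinical laboratory results for subjects will be the data collected at the Week 0 visit immediately prior to study drug administration in Study 1311.5". SAP 6.1 does the same: "The last non-missing measure collected on or before the day of the first dose of study drug injection in Study 1311.5" is the value that "will be used as the Baseline for summary of demographics, disease characteristics and safety analyses". Neither section distinguishes subjects by their Study 1311.5 arm.

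That baseline carries through the SAP:
- Section 11.3 takes laboratory changes and normal-range shift tables from it. The continuous changes are shown separately "for the group of subjects that received Placebo in Study 1311.5" and for those who received risankizumab. No such split is stated for the shift tables.
- Section 11.3.2 takes the liver-test shifts to maximum and to final value from it.
- Section 11.4.2 reads: "Changes from Baseline in Study 1311.5 to each visit and to the final value in vital sign parameters will be summarized". Each blood pressure and heart rate criterion in Table 18 requires both an absolute value and a change from baseline.
- Section 5.1 summarizes safety in a single risankizumab group, whatever the earlier arm.

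Two provisions fix the timing. Protocol inclusion criterion 1 admits "Subjects who have completed all doses of study drug and Week 24 visit of Study 1311.5", and exclusion criterion 4 rules a subject out when "Time elapsed is > 8 weeks since the Week 24 visit in Study 1311.5".

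A later value exists. Protocol Appendix C schedules safety laboratory tests and vital signs at M16-244 Week 0. If the delay is 4 days or less, the Study 1311.5 Week 24 results stand in (footnote a). SAP Table 6 has a Week 0 window, but no analysis uses that value as a baseline.

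**The concern.** The primary objective is the safety and tolerability of risankizumab. For a prior-risankizumab subject, the Study 1311.5 pre-dose value is the last one free of drug, and it is the right reference. For a prior-placebo subject, the last drug-free value is M16-244 Week 0 or its stand-in. Measuring from the start of Study 1311.5 adds a placebo period, and possibly an untreated gap, to the interval that the risankizumab tables describe.

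Errors can go both ways. A shift that was already present at Week 0 is counted in the risankizumab group. A change that arises on drug can be offset by an opposite change before it.

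The SAP starts from the first risankizumab dose elsewhere. Section 11.2.1 item 5 builds its total-risankizumab event summary by "including AEs occurring after the first dose in Study M16-244 for subjects who received Placebo in Study 1311.5". The laboratory and vital-sign analyses have no matching rule.

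**Working it through.** The plan states no figure to reproduce here. It is descriptive, with no power calculation. The check has four parts.

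**1. Interval before the first risankizumab dose.** Inputs: the Week 24 visit (inclusion criterion 1) and a gap g of 0 to 8 weeks (exclusion criterion 4). Time from baseline to first dose = 24 + g, which is 24 weeks (168 days) to 32 weeks (224 days). At M16-244 visit week v, the pre-drug share of the measured interval is (24 + g)/(24 + g + v).

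| Visit week v | g = 0 | g = 8 |
|---|---|---|
| 4 | 24/28 = 86% | 32/36 = 89% |
| 12 | 24/36 = 67% | 32/44 = 73% |
| 24 | 24/48 = 50% | 32/56 = 57% |
| 36 | 24/60 = 40% | 32/68 = 47% |
| 48 | 24/72 = 33% | 32/80 = 40% |
| 52 | 24/76 = 32% | 32/84 = 38% |

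These are shares of time, not of change.

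**2. Table 18, high systolic pressure.** The criterion is a value of at least 180 mmHg and a rise of at least 20 mmHg. Two constructed prior-placebo profiles (1311.5 baseline / Week 0 / on drug):
- 150 / 178 / 181: 181 − 150 = 31, so flagged. From Week 0, 181 − 178 = 3, so not flagged.
- 175 / 150 / 190: 190 − 175 = 15, so not flagged. From Week 0, 190 − 150 = 40, so flagged.

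They show that both errors are possible, not how often they occur.

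**3. Shift tables within the prior-placebo group.** Assumptions, none of them from the documents: a normally distributed parameter with SD 1, upper limit of normal at 1.96 SD, correlation 0.7 between any two visits, drift of d SD between the 1311.5 baseline and Week 0, and no change afterwards (no drug effect).

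Net excess of up-shifts over down-shifts = P(final high) − P(baseline high) = [1 − Φ(1.96 − d)] − [1 − Φ(1.96)]. The correlation cancels in this difference and affects only the separate up and down rates.

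| d | P(final high) − P(baseline high) | Net excess, points | Up / down from 1311.5 baseline | Each way from Week 0 |
|---|---|---|---|---|
| 0 | 2.50% − 2.50% | 0 | 1.67% / 1.67% | 1.67% |
| 0.1 | 3.14% − 2.50% | 0.64 | 2.19% / 1.55% | 2.04% |
| 0.3 | 4.85% − 2.50% | 2.35 | 3.63% / 1.29% | 2.96% |
| 0.5 | 7.21% − 2.50% | 4.71 | 5.74% / 1.02% | 4.11% |

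From a Week 0 baseline the net excess is zero throughout, as it should be with no drug effect. In up-shifts alone, the excess at 0.3 SD is 3.63 − 2.96 = 0.67 points.

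**4. Pooled group (SAP 5.1).** Assume a prior-placebo share of 10 to 30%, and no such excess among the others. At 0.3 SD: 0.10 × 2.35 = 0.24 and 0.30 × 2.35 = 0.71, so about 0.2 to 0.7 points. With the maximum enrolment of 180, that is 0.4 to 1.3 subjects per parameter. At 0.5 SD: 0.5 to 1.4 points, or about 0.8 to 2.5 subjects.

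**The case against.** The choice is consistent between protocol and SAP, matches the feeder-study baseline used for efficacy, and is openly labelled as Study 1311.5. No decision rule depends on it. All of this stands: it is a presentation choice, not a concealed error.

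Much of the safety output is outside its reach. The cut-offs in Tables 15 and 16, the liver and Hy's Law listings and the eDISH plot use absolute values or multiples of ULN. Adverse event tables do not use this baseline either. A reader might infer that the whole safety picture for prior-placebo subjects is distorted. The documents do not support that.

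There are also partial safeguards. SAP 11.4.2 lists the full course for every subject who meets a Table 18 criterion, so the first profile above would explain itself. The second would not be listed on that value, because it is never flagged. By-visit laboratory means split by prior arm may show placebo-period drift. However, the Week 0 window in SAP Table 6 is Day 1 only, so a stand-in result from up to 4 days earlier could fall outside it if days are counted from the first M16-244 dose. No split is stated for vital signs or shift tables.

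SAP 11.3 describes the final value as the last assessment in each treatment period, which might mean shifts shown period by period. Even so, the starting point remains the Study 1311.5 baseline.

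Finally, the Study 1311.5 protocol is not available. That its placebo subjects had no earlier risankizumab is an inference from SAP 11.2.1 item 5, and any gap before entry is untreated time, not placebo.

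**Conclusion.** The point holds in limited form. For prior-placebo subjects, laboratory and vital-sign changes, the laboratory and liver shift tables and the change part of Table 18 mix a nominal 24 to 32 pre-risankizumab weeks with the on-drug period. Pre-drug shifts can be counted in the risankizumab group, and an on-drug change can miss its flag.

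The size is unknown. It depends on the number of prior-placebo subjects and on the drift before entry, and the documents give neither. With no drift, the net shift excess is zero, although individual Table 18 results can still be misclassified. It would be tempting to report a 2.35-point excess as what the planned table will show. That figure assumes 0.3 SD drift and a prior-placebo column that the SAP does not specify for shifts. In the planned pooled group it becomes 0.2 to 0.7 points under the assumed 10 to 30% share.

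Nor is the Study 1311.5 baseline wrong for everyone: for prior-risankizumab subjects it is correct. The case for a change rests on its low cost and its bearing on the primary objective, not on a demonstrated large bias.

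**What to change.** In SAP 6.1, 11.3 and 11.4, with matching wording in Protocol 8.1.6.1:
- For prior-placebo subjects, present change, shift and Table 18 analyses from the last value before the first risankizumab dose. This is M16-244 Week 0, or the Study 1311.5 Week 24 result that stands in for it.
- Show these analyses by prior arm, and keep the Study 1311.5 baseline for prior-risankizumab subjects.
- State that stand-in results taken up to 4 days before Day 1 are mapped to Week 0.
- Keep the present Study 1311.5-baseline tables for continuity with the feeder study and the efficacy analyses.

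The cost is one derived baseline flag and an extra set of tables, with no new data collection. The two prior arms will then have different reference points, which a footnote should state.
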